9.5.1. Primary Efficacy Endpoint

The primary efficacy endpoint is AUC of the NRS pain intensity scores from 0 to 96 hours postoperation using Efficacy Analysis Set. The NRS pain intensity score is collected from the assessment "How much pain are you experiencing right now?" The worst and average daily pain scores are not included in the AUC calculation.

AUC curve is derived using the trapezoidal rule (see formula below) on the pain scores adjusted for opioid pain medication using the observed and imputed values (see Section 9.2.2). AUC will start with the first pain assessment obtained after surgery (arrival at PACU) and use all subsequent pain assessments up to 96 hours post-surgery. Pain scores collected prior to the opioid medication administration or unscheduled are also included in the AUC calculation. Exact assessment time will be used in deriving AUC.

$$AUC = \left\{ \sum_{i=2}^{n} (p_i + p_{(i-1)})(t_i - t_{(i-1)}) \right\} / 2$$

Where p_i is the NRS pain score at time *i* and t_i is the time, in hours, from end of surgery. Note t_i is pain score collected upon PACU arrival. It is the first time NRS score is collected.

In calculating AUC_{0-96} , if the exact 96-hour pain score is not collected, it will be interpolated using the two nearest before and after data points. If the last 96-hour assessment is before 96.0 hours, then the exact 96-hour pain score for the AUC calculation will use this last observation carried forward.

 $AUC_{0.96}$ for pain intensity from 0 to 96 hours will be summarized by treatment group, by surgery type and overall.

Tests for the superiority of treatment effect of EXPAREL versus 0.25% bupivacaine HCl will be based on the following null hypotheses and alternative hypotheses using the Efficacy analysis set and multiple imputation method:

H_o: EXPAREL is not different from 0.25% bupivacaine HCl with respect to AUC for pain intensity

HA: EXPAREL is superior to 0.25% bupivacaine HCl with respect to AUC for pain intensity

A two-sided hypothesis test will be performed at 5% level of significance comparing EXPAREL and 0.25% bupivacaine HCl as follows:

If the upper bound of the 2-sided 95% confidence interval for the least square (LS) means for the difference of AUC₀₋₉₆ (EXPAREL) – AUC₀₋₉₆ (0.25% bupivacaine HCl) is ≥0, then superiority of EXPAREL to 0.25% bupivacaine HCl is not achieved.

• If the upper bound is <0 then declare that the superiority of EXPAREL to 0.25% bupivacaine HCl is achieved.

9.5.2. Secondary Efficacy Endpoints

9.5.2.1. Total postsurgical opioid consumption in oral morphine equivalents from 0 to 96 hours post-surgery comparing EXPAREL to 0.25% bupivacaine HCl

Total postsurgical opioid consumption (OMED mg) will be summarized by treatment group and surgery type using Efficacy Analysis Set. The summary will include number of subjects receiving postsurgical opioids, geometric mean and coefficient of variation (CV%), median, minimum and maximum.

To test for significant difference between EXPAREL and 0.25% bupivacaine HCl, an analysis of covariance (ANCOVA) model with treatment as main effect and investigator site (categorical), age, and height as covariates will be applied to the natural log-transformed total dose. The LS means for EXPAREL and 0.25% bupivacaine HCl, LS mean difference between

EXPAREL and 0.25% bupivacaine HCl, two-sided 95% CI for the LS mean difference, and the two-sided p-value will be reported after back transformation (ie, taking exponential) to the original OMED scale. If a subject does not have postsurgical opioid consumption, a 3.75 mg OMED will be assigned for the ANCOVA analysis using log-transformation.

In addition to the presentation for the between group difference, the percent reduction in total opioid consumption will also be presented similar to Section 9.5.1.

As sensitivity analysis, this endpoint will also be analyzed using the non-stratified Cochran-Mantel-Haenszel test for the row mean score difference with modified ridit scores.

A sample SAS code is as follows.

```
PROC FREQ ;
    TABLES trtp*omed / CMH SCORE=modridit ;
RUN ;
```

Another sensitivity analysis will be carried out in the same way as for the primary analysis using ANCOVA but excluding two subjects described in Section 9.5.1.

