11.3. Method of Assigning Subjects to Treatment

11.3.1. Randomization Scheme

This is a randomized study. Cohort 1 will enroll approximately 60 total subjects undergoing bunionectomy surgery randomized 1:1:1 in the EXPAREL arm, EXPAREL admixed with 0.25% bupivacaine HCl arm (“admix” arm), and bupivacaine HCl arm.

Cohort 2 will enroll approximately 60 total subjects undergoing distal lower extremity surgery, 20 subjects in each treatment arm; EXPAREL arm, EXPAREL admix arm, and bupivacaine HCl arm. Subjects will be randomized 1:1:1 to treatment groups, by stratifying by surgery grouping. The randomization code will be generated by a centralized randomization system, which will also be used to communicate subject randomizations to study sites. All randomized subjects will have

both a unique subject identifier and a unique randomization code. No subject or randomization code identifiers will be reused once assigned.

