15. STATISTICAL METHODS

A comprehensive statistical analysis plan (SAP) will be finalized for this study prior to database lock. Demographic and baseline characteristics will be summarized descriptively by treatment group for all subjects who receive study drug. Efficacy and safety endpoint analyses will be described in the SAP.

Efficacy data will be analyzed by randomized treatment group. Superiority of treatment with EXPAREL compared with bupivacaine HCl will be determined using analysis of variance (ANOVA) with treatment as main effect for the primary efficacy endpoint of AUC of the NRS pain intensity scores from 0 to 96 hours post-surgery. Additional factors such as site or surgery type may be included to adjust the model if deemed necessary. Other efficacy endpoints will be analyzed using ANOVA, logistic regression model, chi-square tests, and Kaplan-Meier and log-rank tests, as appropriate.

Safety and pharmacokinetic endpoints will be summarized descriptively by actual treatment received.

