15.3. Determination of Sample Size

The sample size was calculated based on the primary efficacy endpoint of the AUC of the NRS pain intensity scores from 0 through 96 hours post-surgery comparing EXPAREL to bupivacaine HCl.

The sample size for Cohort 1 was based on the number of subjects necessary to characterize the PK following administration.

Cohort 1 and Cohort 2 subjects will be combined within treatment groups for the efficacy and safety analyses; therefore, the overall sample size was based on the primary efficacy endpoint of the AUC of the NRS pain intensity scores from 0 through 96 hours post-surgery. Assuming a 2-sided 0.05 alpha, common standard deviation (SD) of 170 a sample size of 40 subjects for EXPAREL and 40 subjects for bupivacaine HCl should have at least 90% power to detect a true difference of 150-units in the AUCs. Therefore, since Cohort 1 will have 60 subjects

(20 EXAPREL, 20 EXPAREL admixed with bupivacaine HCl and 20 bupivacaine HCl), Cohort 2 will need to enroll 60 subjects (20 EXAPREL, 20 EXPAREL admixed with bupivacaine HCl and 20 bupivacaine HCl) to meet the total requirements.

An efficacy interim analysis will occur when approximately 60 subjects have enrolled and provided complete data for the primary efficacy outcome.

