4. STUDY OVERVIEW

This is a Phase 3, multicenter, randomized, double blind, active controlled study in approximately 120 subjects undergoing lower extremity surgeries. This study will have 2 cohorts. Both cohorts will enroll in parallel.

Randomization

Cohort 1 will enroll about 60 subjects undergoing bunionectomy to obtain information on PK profile, PD, efficacy and safety. Subjects in this cohort will be randomized (1:1:1) to receive combined sciatic (in popliteal fossa) and saphenous (in the adductor canal) nerve block with EXPAREL, EXPAREL admixed with 0.25% bupivacaine HCl, or 0.25% bupivacaine HCl.

Cohort 2 will enroll about 60 subjects to obtain information on efficacy and safety. Subjects in this cohort will receive combined sciatic (in popliteal fossa) and saphenous (in the adductor canal) nerve block. Subjects will be randomized (1:1:1) to receive EXPAREL, EXPAREL admixed with 0.25% bupivacaine HCl, or 0.25% bupivacaine HCl, by stratifying by each surgery grouping.

Treatment

For both Cohorts 1 and 2, subjects randomized to the EXPAREL arm will receive 20 mL (266 mg) EXPAREL mixed with 20 mL saline; subjects randomized to EXPAREL admix arm will receive 20 mL (266 mg) EXPAREL admixed with 20 mL (50 mg) 0.25% bupivacaine HCl; subjects randomized to the 0.25% bupivacaine HCl arm will receive 40 mL (100 mg) 0.25% bupivacaine HCl.

Block Procedure

Subjects may be lightly sedated with 1 to 2 mg of midazolam intravenously (IV) before the block procedure. The study drug (EXPAREL, EXPAREL admixed with 0.25% bupivacaine HCl, or 0.25% bupivacaine HCl) will be administered under ultrasound guidance 90 min (\pm 30 min) prior to surgery.

Breakthrough Pain Medication

All opioid and other analgesics administered post-surgery through post-operative day 14 (POD14) will be recorded.

For the initial treatment of breakthrough pain, subjects may receive acetaminophen or NSAIDs.

If the initial pain treatment (acetaminophen or NSAIDs) is insufficient for pain relief, immediate release PO oxycodone may be administered in a stepwise approach:

- Initial dose of 5 mg oxycodone may be offered.
- If the initial opioid dose is insufficient for pain relief, 10 mg oxycodone may be offered.

If a subject is unable to tolerate PO medication or the PO oxycodone pain relief is insufficient, IV morphine (initiated at 2 mg) or hydromorphone (initiated at 0.2 mg) may be administered.

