** Note the value for the random seed is fixed to be 156799 so that the results are reproducible, MIN=0 and MAX=10 are to bound the imputed VAS score within 0-10, ROUND=0.1 is to round the imputed NRS score with 1 decimal place. The Box-Cox transformation is to reduce the skewness of the data distribution **

```
proc mi data=adef seed=156799 nimpute=50 out=output_step1 min=0
max=10 round=0.1 minmaxiter=10000;
```

```
by treatment;
mcmc chain=multiple impute=full initial=em prior=jeffreys
nbiter=2000 niter=1000;
var t6 t12 t18 t24 t30 t36 t42 t48 t54 t60 t66 t72 t78 t84 t90
t96 ;
transform boxcox (t6 t12 t18 t24 t30 t36 t42 t48 t54 t60 t66
t72 t78 t84 t90 t96 / c=0.5 lambda=0) ;* this is log(t+0.5)
transformation ;
```

```
run;
```

** Step (c) calculates AUC for each subject in the imputed data set (with _IMPUTATION_ =1 to 50) **;

** Step (d) analyzes AUC using ANCOVA model for each imputed data set and derives LSM, SE for each treatment group and LSM, SE, and 95% CI for the between treatment difference **;

```
ods output Diffs=diff LSMeans=lsm ;
proc genmod data=auc1;
    by _imputation_;
    class trtpn siteid;
    model aval=trtpn siteid age height / dist= normal
    link=identity;
    lsmeans trtpn / diff cl alpha=0.05 ilink;
    ods output LSMeans=lsm;
    ods output Diffs=diff;
```

run;

```
** Step (e) synthesizes LSMs and SEs derived from the 50 imputed data sets **;
ods output ParameterEstimates=lsmdif;
proc mianalyze data=diff alpha=0.05;
    modeleffects estimate;
    stderr stderr;
run;
ods output ParameterEstimates=lsmeans;
proc mianalyze data=lsm alpha=0.05;
    by trtpn;
    modeleffects estimate;
    stderr stderr;
run;
```

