9.5.2.2. Time to first postsurgical opioid consumption comparing EXPAREL to 0.25% bupivacaine HCl

Time to first opioid consumption will be calculated in hours as the date and time of the first opioid medication taken post-surgery minus the date and time of end of surgery. If a subject does not have an opioid usage post-surgery, the time to first opioid consumption will be censored at the date of End of Study. For this derivation, the opioid consumption recorded on both Breakthrough Pain Medications and Prior/Concomitant Medications CRF pages will be considered.

Time to first opioid usage will be analyzed by the Kaplan-Meier survival analysis. Median time and the log-rank test comparing EXPAREL and 0.25% bupivacaine HCl will be presented. The log-rank test will be stratified by the age and height group (Section 9.5.3). Cox proportional hazards regression with treatment (EXPAREL, EXPAREL admixed with 0.25% bupivacaine, and 0.25% bupivacaine HCl) as factors and categorical investigator site, continuous age and height as covariates will also be performed. The number (and %) of subjects with opioid pain medication post discharge as well as the number (and %) of subjects without opioid pain medication post discharge will be presented for each treatment group.

9.5.2.3. AUC of the NRS pain intensity scores from 0 to 96 hours post-surgery comparing EXPAREL to EXPAREL admixed with 0.25% bupivacaine HCl

To examine differences between EXPAREL and EXPAREL admixed with 0.25% bupivacaine HCl, the same ANCOVA model as for the primary efficacy endpoint will be used. The LS mean difference between EXPAREL and EXPAREL admixed with 0.25% bupivacaine HCl groups, and two-sided 95% CI for the LS mean difference will be presented.

In addition to the presentation of the difference, the percent reduction in AUC will also be presented. The % reduction is derived as follows,

% Reduction = $\{LS Means_{EXP+Bup} - LS Means_{EXPAREL}\}/LS Means_{EXP+Bup}$.

9.5.2.4. Duration of the motor block comparing EXPAREL to EXPAREL admixed with 0.25% bupivacaine HCl (Cohort 1 only)

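### The pooled AUC and opioid models adjust for site, age and height but leave out the randomisation stratum (cohort and surgery grouping) and the baseline pain score

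*SAP*

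**What the plan says.** **Randomisation.** Protocol 11.3.1 gives Cohort 1, all bunionectomy, its own 1:1:1 allocation. For Cohort 2 it says: "Subjects will be randomized 1:1:1 to treatment groups, by stratifying by surgery grouping". SAP 4 agrees ("or 0.25% bupivacaine HCl, by stratifying by each surgery grouping"). Protocol 15.3 then pools them: "Cohort 1 and Cohort 2 subjects will be combined within treatment groups for the efficacy and safety analyses".

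**Models.**
- AUC, code step (d) in SAP 9.2.2: "model aval=trtpn siteid age height / dist= normal". For EXPAREL against the admixture, SAP 9.5.2.3 says "the same ANCOVA model as for the primary efficacy endpoint will be used".
- Total opioid use, SAP 9.5.2.1: "an analysis of covariance (ANCOVA) model with treatment as main effect and investigator site (categorical), age, and height as covariates will be applied". Its rank-based sensitivity test is unstratified.
- Time to first opioid, SAP 9.5.2.2: a Cox model with site, age and height, and a log-rank test stratified by age and height group. SAP 9.5.3 cuts these at 45 years and 165 cm.

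**Where surgery type appears.** Protocol 15 left it open: "Additional factors such as site or surgery type may be included to adjust the model if deemed necessary". Protocol 15.6.3 adds a surgery-stratified sensitivity analysis for the primary endpoint only. In the SAP text available to this review, surgery type is used for descriptive summaries (9.5, 9.5.1, 9.5.2.1) and as a subgroup (9.5.3), never as an adjustment term.

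**Baseline pain.** Worst and average pain over the previous 30 days are recorded before the block (Protocol 13.2.3). SAP 9.4.2 only tabulates them.

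**The concern.** Stratified randomisation balances the arms on surgery, which makes the treatment difference less variable when surgery predicts pain. A model that leaves the stratum out keeps the between-surgery variation in its residual. Its standard error is then larger than the true spread of the estimate, and the test rejects less often than its nominal level. The log-rank test has the same mismatch: it is stratified by two factors that played no part in the randomisation and not by the one that did.

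Precision matters most for the secondary endpoints. SAP 9.5 tests in fixed order: AUC, total opioid use, time to first opioid, then the two comparisons with the admixture. A missed opioid result stops everything after it, and the sample size (Protocol 15.3, SAP 10) is justified for the primary endpoint only.

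Baseline pain is a separate matter. It is not a randomisation factor, so omitting it is a lost chance to reduce variance, not a mismatch with the design.

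The SAP also disagrees with itself on surgery type. Section 9.5 rules out statistical analysis within a surgery type, while 9.5.3 repeats the primary and first secondary analyses by surgical type.

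**Working it through.** **Inputs** (Protocol 15.3, SAP 10): SD 170, 40 per arm, difference 150, two-sided alpha 0.05, power at least 90%.

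**The plan's figure.** SE = 170 × √(2/40) = 38.0. Noncentral t power on 78 df is 97.4% (normal approximation 97.6%), which agrees with at least 90%. If the true difference were 100, power would be 73.8%.

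**Assumed variance explained.** The documents give no R². Let R² be the share of variance explained beyond site, age and height. Then:
- adjusted SE = 38.0 × √(1 − R²)
- sample-size equivalent = 1/(1 − R²)
- true size of a nominal 5% test that omits a balanced stratum = 2 × [1 − Φ(1.96/√(1 − R²))]

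| Assumed R² | SE with term | Power at 150 | Power at 100 | Size if balanced stratum omitted |
|---|---|---|---|---|
| 0 | 38.0 | 97.4% | 73.8% | 5.0% |
| 5% | 37.1 | 97.9% | 76% | 4.4% |
| 10% | 36.1 | 98.4% | 78% | 3.9% |
| 20% | 34.0 | 99.2% | 83% | 2.8% |

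**What R² could surgery supply?** For a two-level factor with non-bunionectomy share p and group difference d, R² = p(1 − p)d²/170². One NRS point over 96 hours is d = 96. The share p cannot exceed 50%, since 60 of the 120 subjects are bunionectomy by design.

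| d | p = 10% | p = 20% | p = 50% |
|---|---|---|---|
| 48 | R² 0.7% | 1.3% | 2.0% |
| 96 | R² 2.9%, SE 37.5 | 5.1%, SE 37.0 | 8.0%, SE 36.5 |

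The d = 96 row is worth 1/(1 − R²) − 1, about 3%, 5% and 9% more patients.

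**Baseline pain alone.** R² = ρ². Assumed correlations with AUC of 0.2, 0.3 and 0.4 give R² of 4%, 9% and 16%, and SE of 37.2, 36.3 and 34.8.

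**Simulation of the SAP's linear model.** It used 120 subjects, three arms balanced within a two-level stratum, six sites, and treatment, site, age and height in the model, with and without the stratum. The bunionectomy share was 50% or 90%. There were 3,000 null and 1,500 alternative runs per scenario, so the Monte Carlo error on a 5% rate is √(0.05 × 0.95/3000), about 0.4 points.

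| Stratum R² | Type I error, omitted, site unrelated to stratum |
|---|---|
| 10% | 4.2% |
| 20% | 2.7–2.9% |
| 30% | 2.0–2.3% |

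- With the stratum included, type I error was 4.5–5.4% over these R² values.
- When site largely tracked the stratum, the omitting model gave 4.2–5.1%, so little was lost.
- At R² 20%, 50% share and unrelated site, the omitting model reported a mean SE of 39.2 against an actual spread of 34.9. With the stratum it reported 35.0 against 34.7.
- Mean estimates under the null stayed within 3 units of zero.
- Power at 150 was 97.0–99.6% for R² of 10% or more, with or without the term.

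Nothing was computed for log opioid dose, the Cox model or the log-rank test.

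**The case against.** The strongest reply is that the practical gain is small. SAP 5 reports that bunionectomy dominates enrolment, so shares of 10% to 20% are more relevant than 50%. With differences of 48 to 96 units, R² is then 0.7% to 5.1%, the SE moves from 38.0 to between 37.9 and 37.0, and power at 100 units goes from 73.8% to between 74% and 76%. An R² of 20% from surgery alone would need the groups to differ by 190 to 253 units at those shares, about 2.0 to 2.6 NRS points held for four days. Nothing in the documents supports that. Only select sites enrol Cohort 1 (Protocol 9.1), so site may already absorb part of the cohort effect. All of this stands and limits the size of the point.

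Second, part of SAP 9.5.1 was not available to this review, and 9.5.4 refers to it for the model specification and a sensitivity analysis. The AUC point therefore rests on the code in 9.2.2, which the SAP calls pseudo-code. For the same reason, no conclusion can be drawn about whether the protocol's surgery-stratified sensitivity analysis was kept. The opioid ANCOVA, Cox and log-rank specifications are visible, and the omission there is certain, though its size has not been computed.

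Third, the protocol permits surgery type as a factor and does not require it, so the SAP breaks no commitment. That is correct. The criticism is of the choice, not of compliance.

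Fourth, collapsing to bunionectomy against other surgery could lose the cohort distinction. That is a fair caution about the remedy, and the fix below allows for it.

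**Conclusion.** The concern holds. The visible pooled models and the log-rank test do not follow the randomisation, and pain scores already collected go unused. The point is clearest for total opioid use and time to first opioid.

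For AUC the cost is intervals that are too wide and a conservative test, with no bias in the difference and no inflated type I error. The likely gain from surgery is a few per cent of sample size, depending on the assumed group difference, the surgery mix and how far site stands in for cohort. Baseline pain could add a similar or larger amount if it correlates with AUC at 0.2 to 0.4, also an assumption. The primary test does not need the gain at 150 units. It helps if the true effect is smaller. This should be changed, but the trial's validity does not depend on it. Motor-block duration is measured in Cohort 1 only and is unaffected.

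**What to change.** Before unblinding, amend the SAP as follows:

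1. Add the randomisation stratum to the AUC and total-opioid ANCOVAs and to the Cox model. Define it as cohort plus surgery grouping, collapsing sparse groupings to bunionectomy against non-bunionectomy, which SAP 5 already defines. Keep Cohort 1 distinct from any Cohort 2 bunionectomy subjects where numbers allow.
2. Stratify the time-to-first-opioid log-rank test by that stratum in place of age and height group.
3. Add baseline average 30-day pain to the same ANCOVA and Cox models, described as a precision covariate.
4. Keep the present site, age and height models as sensitivity analyses.
5. Reconcile SAP 9.5 with 9.5.3 on whether inferential analyses by surgery type are done.

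The cost is SAP wording, matching code and a few degrees of freedom out of about 120 subjects. No new data are needed.

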8.1.2. Secondary Endpoints

- 1. Total postsurgical opioid consumption in oral morphine equivalents from 0 to 96 hours postsurgery comparing EXPAREL to 0.25% bupivacaine HCl
- 2. Time to first postsurgical opioid consumption comparing EXPAREL to 0.25% bupivacaine HCl
- 3. AUC of the NRS pain intensity scores from 0 to 96 hours post-surgery comparing EXPAREL to EXPAREL admixed with 0.25% bupivacaine HCl
- 4. Duration of the motor block comparing EXPAREL to EXPAREL admixed with 0.25% bupivacaine HCl (Cohort 1 only)
- 5. Proportion of opioid-free subjects through 24, 48, 72, and 96 hours from end of surgery

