9.5. Efficacy Analysis

For Primary and Secondary Efficacy Analyses, descriptive statistics that are appropriate for the efficacy variable will also be shown by surgical type, but no statistical analyses will be performed within a surgery type. All efficacy analyses will be performed using the Efficacy analysis set.

Unless specified otherwise, all confidence interval will be 2-sided with 95% confidence. All statistical comparison will be 2-sided at alpha=0.05 level. The leading statistical comparison is between EXPAREL and 0.25% bupivacaine HCl for the primary and first two secondary endpoints and between EXPAREL and EXPAREL admixed with 0.25% bupivacaine HCl for the third and fourth secondary endpoints, though all 3 pairwise comparisons (EXPAREL vs 0.25% bupivacaine HCl, EXPAREL vs EXPAREL admixed with 0.25% bupivacaine HCl, and EXPAREL admixed with 0.25% bupivacaine HCl, and EXPAREL admixed with 0.25% bupivacaine HCl, will be presented.

To control for the overall Type-I error rate for the multiple comparisons, the statistical tests will be conducted in the hierarchical order as follows. See also Section 8.1 for detail.

- 1. Primary endpoint: EXPAREL vs 0.25% bupivacaine HCl
- 2. First secondary endpoint: EXPAREL vs 0.25% bupivacaine HCl
- 3. Second secondary endpoint: EXPAREL vs 0.25% bupivacaine HCl
- 4. Third secondary endpoint: EXPAREL vs EXPAREL admixed with 0.25% bupivacaine HCl

5. Fourth secondary endpoint: EXPAREL vs EXPAREL admixed with 0.25% bupivacaine HCl

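### The sample rank-test code for total opioid consumption is not restricted to two arms; run on the three-arm Efficacy set, it would not give the EXPAREL versus bupivacaine HCl comparison

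*SAP*

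**What the plan says.** The first secondary endpoint (SAP 8.1.2, item 1) is total postsurgical opioid consumption in oral morphine equivalents, EXPAREL against 0.25% bupivacaine HCl. SAP 9.5.2.1 opens its main analysis with "To test for significant difference between EXPAREL and 0.25% bupivacaine HCl" and specifies an ANCOVA on log dose. In that ANCOVA, subjects with no opioid use are assigned 3.75 mg.

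As a sensitivity analysis, "this endpoint will also be analyzed using the non-stratified Cochran-Mantel-Haenszel test for the row mean score difference", using modified ridit scores. The code, introduced as a sample, is a bare `PROC FREQ` with "TABLES trtp*omed / CMH SCORE=modridit". It has no `DATA=`, `WHERE` or `BY`. A second sensitivity analysis repeats the ANCOVA without two subjects.

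SAP 9.5 sets the context:
- The leading comparison is "between EXPAREL and 0.25% bupivacaine HCl for the primary and first two secondary endpoints".
- Other contrasts are to be shown too, "though all 3 pairwise comparisons". No overall three-arm test is named.
- "All efficacy analyses will be performed using the Efficacy analysis set". Protocol 15.4 defines that set as randomized subjects who undergo the planned surgery, so it includes the admix arm.

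**The concern.** A row-mean-score test compares all rows of the table. With three treatment levels it is an omnibus test of EXPAREL, admix and bupivacaine HCl, and it returns a single p-value.

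The sample code for the primary model (SAP 9.2.2) also keeps all arms, but its `lsmeans ... / diff` statement extracts each pairwise difference. The `PROC FREQ` call has no counterpart, so the p-value for the intended pair would never be produced.

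This matters because of what the rank test is for. The main ANCOVA, and its repeat without two subjects, both rest on the 3.75 mg assignment. The rank test is the only inferential test shown for total dose that does not. If it is significant because of the admix arm, or non-significant because a degree of freedom was spent on that arm, a report could describe the EXPAREL versus bupivacaine result as more or less robust than it is.

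**Working it through.** **Inputs.** Three arms, 1:1:1 (SAP 4); 40 per arm (SAP 10); two-sided alpha 0.05 (SAP 9.5). The documents give no effect size, SD or power for opioid dose, so every shift below is an assumption, in SD units of log dose.

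**The plan's own figure.** The only design figure is for the primary endpoint: at least 90% power for a difference of 150 with SD 170. Check: 150 / (170 × √(2/40)) = 3.95; 3.95 − 1.96 = 1.99; power about 97.6%. The claim holds. It has no bearing on the rank test beyond the 40 per arm.

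**The statistic.** With one stratum and modified ridit scores, rank/(N+1),

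Q = (N − 1) × Σ nᵢ(r̄ᵢ − r̄)² / Σ(r − r̄)², referred to chi-square with (rows − 1) df.

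This equals the Kruskal-Wallis statistic; the two agreed when coded side by side. Three rows give 2 df and two rows give 1 df.

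**Constructed example.** EXPAREL and bupivacaine have identical values (1 to 40 each), and every admix value is 12 lower. Mean ranks are 70.7, 70.7 and 40.1 against an overall 60.5; the variance of the ranks is 1199.4.
- Three arms: Q = 119 × 40 × (10.2² + 10.2² + 20.4²) / (120 × 1199.4) = 20.6 on 2 df, p = 0.00003.
- EXPAREL and bupivacaine only: Q = 0 on 1 df, p = 1.

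**Rejection rates.** These were simulated with normal log-doses, 40 per arm and 4,000 or 5,000 trials per pattern. A large-sample check uses noncentrality λ = (3/π) × 40 × Σ(μᵢ − μ̄)², with 2 df (three-arm) or 1 df (two-arm).

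| Means (EXPAREL, admix, bupivacaine), SD | Three-arm, simulated | Three-arm, formula | Two-arm, simulated | Two-arm, formula |
|---|---|---|---|---|
| 0, 0, 0 | about 5% | 5% | about 5% | 5% |
| 0, 0.25, 0 | about 17% | λ = 1.59: 19% | about 5% | 5% |
| 0, 0.6, 0 | about 77% | λ = 9.17: 78% | about 5% | 5% |
| 0, 0.25, 0.5 | about 46% | λ = 4.77: 48% | about 57% | λ = 4.77: 59% |
| 0, 0, 0.5 | about 59% | λ = 6.37: 61% | about 58% | λ = 4.77: 59% |

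In the fourth row both tests have the same λ, and the loss of power comes entirely from the extra degree of freedom. In the last row power is similar, but the two tests still disagree on significance in roughly one trial in six.

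**Other distributional assumptions.** With log-normal doses rounded to 7.5 mg steps and 10% opioid-free, EXPAREL equal to bupivacaine, and admix shifted by 0, 0.25, 0.5, 0.75 and 1.0 log-SD, the three-arm test rejects in 4.9%, 13.2%, 41.5%, 76.3% and 96.0% of trials. The two-arm test rejects in 4.4% to 5.2% throughout.

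**The case against.** The best defence is that the three-arm run is inferred. The code is labelled a sample and names no input data set, so a programmer could supply two arms. The section heading, the endpoint definition and SAP 9.5 all point to pairwise testing. This stands as far as intent goes: the text shows a two-arm intent. But the population the SAP names has three arms, and neither the sentence nor the code says to drop one. The call followed literally gives the wrong test.

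Second, the large figures depend on admix departing from both other arms. The only evidence in the documents points elsewhere: preliminary pilot results in Protocol 11.4, from a sciatic block alone, found opioid consumption similar with EXPAREL 266 mg and the admixed groups. That resembles the last row of the table, where power is not lost. This also stands, and it is why the result is given as a range.

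A reader might go further in three ways that the documents do not support:
- *The confirmatory error rate is inflated.* The test lies outside the hierarchy in SAP 9.5, and the ANCOVA is untouched.
- *The rank test as coded can say nothing about EXPAREL versus bupivacaine.* It holds its 5% level when all arms are equal, and it detects the difference about as often as the two-arm test when admix matches EXPAREL. It misleads when admix differs from both or lies between them.
- *Nothing else planned avoids the 3.75 mg value.* SAP 9.5.2.1 confines that value to the ANCOVA. The median, the range and the count of opioid users do not need it, nor do the separate endpoints of time to first opioid and proportion opioid-free.

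**Conclusion.** The point holds as a mismatch between sample code and stated intent in a sensitivity analysis of a secondary endpoint. Run on the Efficacy set, the call yields a 2-df omnibus test and no p-value for the intended pair.

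With EXPAREL and bupivacaine equal, the chance of apparent support runs from about 5% (admix the same) to about 77% (admix 0.6 SD away). With admix midway between arms 0.5 SD apart, power drops from about 57% to about 46%. With admix equal to EXPAREL it is essentially unchanged. The existence of the problem follows from the SAP text; its size rests on assumed log-dose shifts and 40 per arm. The consequence is a possibly misleading robustness statement, so this is a minor correction that is worth making.

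**What to change.** In SAP 9.5.2.1:
1. Add a `WHERE` statement limiting `trtp` to EXPAREL and 0.25% bupivacaine HCl. If the restriction is made upstream, name the two-arm input data set.
2. Repeat the call for each other pair to be presented under SAP 9.5.
3. State that the reported result is the 1-df row-mean-score p-value for the named pair.

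The cost is one line of code and one sentence of text, with no change to data, design, sample size or the testing hierarchy. It is best made before unblinding, so that the choice between the three-arm and two-arm p-values cannot depend on the results.
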